Considering both the frequency of comorbidity between fibromyalgia and IBS, as well as the frequent presence of non-specific gastrointestinal symptoms in patients with fibromyalgia who might be susceptible to be treated with probiotics, the objective of this trial is to assess the efficacy and tolerability of VSL#3 in patients with fibromyalgia and gastrointestinal symptomatology.

SUBJECTS AND METHODS

Inclusion criteria:

- To have been diagnosed with fibromyalgia, diagnosis that will be confirmed at the time of beginning the screening of patients using the ACR 2016 criteria (Wolfe 2016)
- 18 years of age or older.

- Agreement to voluntarily participate in the study by signing informed consent.
- Be willing to, and do not need under medical criteria, to modify the treatment previously received for fibromyalgia, both of pharmacological and non-pharmacological type, and not change the habits of life, especially about the habitual diet, during the trial's duration
- To regularly suffer (two or more times by week) from three or more of the following symptoms: abdominal pain, abdominal bloating, meteorism, flatulence, nausea, dyspepsia, eructation, constipation and/or diarrhea.

Exclusion criteria:

- To suffer severe mental illness other than major depression.
- To suffer severe renal, hepatic or cardiovascular organic disease that, at the discretion of the investigator, could interfere the participation in the study.
- To suffer any chronic gastrointestinal disease other than irritable bowel syndrome such as inflammatory bowel disease, active gastroduodenal ulcer or colorectal carcinoma.
- Pregnancy or breastfeeding.

Outcome variables:

The severity of the following types of gastrointestinal symptoms: abdominal pain, abdominal bloating, meteorism, flatulence, constipation, diarrhea, nausea, eructation, and dyspepsia will be evaluated using a Visual Analogue Scale (VAS).

The primary endpoint will be the mean severity of the three main gastrointestinal symptoms reported by patients with fibromyalgia, i.e. abdominal pain, abdominal bloating and meteorism.

A seven points, Likert-type scale, the Patient Global Improvement Scale (PGI) will be used to assess the relief of patients' general symptomatology.

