Fibromyalgia Impact Questionnaire Revised (FIQR). This instrument was created to assess the overall symptoms related to fibromyalgia,¹⁷ a modified version having been created in 2009;¹⁸ the validated Spanish version will be used.¹⁹ The total score of the FIQR, assessed through various visual analogue scales, ranges from 0 to 100, and the higher the score, the greater the severity of fibromyalgia. It will allow checking whether an eventual improvement in the gastrointestinal symptoms is reflected in a smaller impact of the symptomatology associated with fibromyalgia.

Insomnia Severity Inventory (ISI). It is a brief questionnaire, composed of seven items evaluated on Likert-type scales, which allows assessing the severity of insomnia. Its total score can range from 0 to 28 points; the higher the score obtained, the greater the severity of insomnia. Since poor sleep quality is also a symptom frequently associated with fibromyalgia it will be used to check whether an eventual improvement in gastrointestinal symptoms is reflected in a better quality of sleep. The validated Spanish version of the questionnaire will be used.²⁰

9-item Patient Health Questionnaire (PHQ-9). It is a brief questionnaire whose objective is to evaluate depressive symptoms. It consists of 9 items evaluated using Likert-type scales. Its total score ranges from 0 to 27 points: the higher the score reached, the greater the severity of the depression. Since depression is also a symptom frequently associated with fibromyalgia it will be used to check whether an eventual improvement in gastrointestinal symptoms is reflected in an improvement in depressive symptomatology. A validated Spanish version of the questionnaire will be used.²⁰

Short-Form Health Survey SF-36. It is multi-item generic health survey intended to evaluate general health concepts not specific to any age, disease or treatment group. It measures 8 health domains: physical functioning, role physical, bodily pain, general health, vitality, social functioning, role emotional and mental health that can also be condensed in two summary measures: the Physical Component Summary (PCS) and the Mental Component Summary (MCS). The validated Spanish version will be applied²⁴.

Study development:

The period between the initial recruitment of patients and their entry into the trial will be two weeks; during this period, the subjects' suitability to be included in the study will be assessed.

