The treatment will consist of the intake of 1 sachet of VSL#3 or matching placebo twice a day during 12 weeks. The assignment of the subjects to the group that will receive the active product or the placebo will be randomized.

On the day of initiation of treatment, the following questionnaires will be administered: VAS of abdominal pain, abdominal bloating, meteorism, flatulence, constipation, diarrhea, nausea, eructation and dyspepsia, FIQR, ISI, PHQ-9, PGI and SF-36.

VAS of gastrointestinal symptomatology will be filled weekly by the patients during the first 4 weeks of the trial and every 2 weeks between weeks 4 and 12 of the trial. At week 12, FIQR, ISI, PHQ-9 and quality of life questionnaire will also be completed again. PGI will be filled on weeks 4, 8, and 12.

At the end of the treatment period, patients will be monitored at 4, 12 and 24 weeks thereafter; these visits will measure VASs of gastrointestinal symptoms, FIQR, PGI and SF-36.

Adverse effects potentially associated with treatment will be collected at each visit through an open question system. Also, during the 12 weeks of treatment the medication packages will be collected to control therapeutic compliance.

Calculation of sample size and assessment of results

Given the absence of previous intervention studies in this area and, in general, limited information on this aspect of fibromyalgia, this should be considered a pilot study. To this consideration should be added the limitation as to the recruitment of patients by the participating sites. Thus, the calculation of the sample size is based on the feasibility of recruiting them. The recruitment of 120 patients has been estimated as a reasonable attainable goal.

The results obtained will be analyzed by applying the Student t test for independent samples to compare the data between the subjects who received placebo and those who received active product and with a two-way analysis of variance to compare the data in the subgroups of patients treated with placebo and with VSL#3..

References:

1. Clauw DJ. Fibromyalgia and related conditions. Mayo Clin Proc 2015; 90:680-692.
2. Yunus MB. The prevalence of fibromyalgia in other chronic pain conditions. Pain Res Treat 2012; 2012:584373.

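### Tolerability is part of the objective, but the adverse event rule collects only what is thought possibly due to treatment, so a judgement of cause can keep events out of the record

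*Combined protocol and SAP*

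**What the plan says.** The end of the introduction states that "the objective of this trial is to assess the efficacy and tolerability of VSL#3 in patients with fibromyalgia and gastrointestinal symptomatology". Tolerability is therefore an aim of the trial.

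The section Study development contains the one collection rule in the text: "Adverse effects potentially associated with treatment will be collected at each visit through an open question system". Nothing elsewhere extends this to events regardless of cause. The text does not say who judges a possible association, by what criterion, or whether the judgement comes before or after recording.

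Other data are collected with no condition on cause. On the nine gastrointestinal symptoms, "VAS of gastrointestinal symptomatology will be filled weekly by the patients during the first 4 weeks of the trial", and then every two weeks to week 12. On the questionnaires, "At week 12, FIQR, ISI, PHQ-9 and quality of life questionnaire will also be completed again". PGI is completed at weeks 4, 8 and 12. For the follow-up at 4, 12 and 24 weeks after treatment, "these visits will measure VASs of gastrointestinal symptoms, FIQR, PGI and SF-36".

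The comparison is randomised against a matching placebo: "The assignment of the subjects to the group that will receive the active product or the placebo will be randomized". The section on sample size calls the trial a pilot and sets its size by feasibility: "The recruitment of 120 patients has been estimated as a reasonable attainable goal". The allocation ratio is not given.

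**The concern.** The qualifier sits in the collection clause. An event that the patient or the investigator puts down to something else need not be written down at all. An event never recorded cannot be recovered by later analysis, whereas an opinion on relationship can be added at any time to a complete record.

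A filter at this point is also unnecessary. The purpose of a randomised placebo arm is to show whether an event is more frequent on the product than in the background, without anyone having to guess the cause of each case. The guess would be poorly informed here: the protocol itself says that there are no previous intervention studies in this area.

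What is at stake is the tolerability half of the objective. In a pilot the event record is a main source for it, and the natural statement from such a record (none of these events was seen, so the incidence is probably below some limit) holds only if the share of events reaching the record is known.

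**Working it through.** The plan gives no figure on this point, so there is nothing to reproduce. The check has two parts: a reading of the text, and an illustration of what incomplete recording does to the conclusions.

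**Reading.** Four elements, side by side:

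- Objective (end of introduction): tolerability is included.
- Collection rule (Study development): limited to effects possibly linked to treatment.
- Scales and questionnaires (Outcome variables; Study development): no condition on cause. Worsening symptoms, sleep, mood, pain or general health is scored in both arms.
- Nature of those instruments: they produce scores, not event records. The SF-36, for example, is described thus: "It is multi-item generic health survey intended to evaluate general health concepts not specific to any age, disease or treatment group". During treatment, FIQR, ISI, PHQ-9 and SF-36 are scheduled only at the start and at week 12, and none of them is scheduled at early withdrawal.

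The scales therefore cover much of the ground. They do not cover discrete events, in particular unexpected or serious events and events that lead to withdrawal.

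**Inputs for the illustration.**

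- Total of 120 patients: from the protocol.
- n = 60 on product: assumed (1:1 allocation); 50 to 70 is also shown.
- a = share of true events judged possibly associated and so recorded: assumed, at 1, 0.9, 0.75 and 0.5. The documents give no basis for any value.
- At most one event of a given kind per patient, each recorded independently.

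**(1) No event recorded.** The recorded incidence is a × p, where p is the true incidence. The one-sided 95% upper limit for p is (1 − 0.05^(1/n)) / a. With n = 60, 1 − 0.05^(1/60) = 0.0487.

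| a | Upper limit, n = 60 |
|---|---|
| 1 (all-cause) | 0.0487 = 4.9% |
| 0.9 | 0.0487/0.9 = 5.4% |
| 0.75 | 0.0487/0.75 = 6.5% |
| 0.5 | 0.0487/0.5 = 9.7% |

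For n = 50 the limit is 5.8% with a = 1 and 11.6% with a = 0.5. For n = 70 it is 4.2% and 8.4%. No incidence is assumed, and the direction is fixed: for a given n, a lower pass share always raises the limit.

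**(2) A harm with an assumed 2% incidence.** The chance that it is recorded at least once is 1 − (1 − 0.02a)^60, and the expected number of records is 60 × 0.02 × a.

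| a | Chance of at least one record | Expected records |
|---|---|---|
| 1 | 70% | 1.20 |
| 0.9 | 66% | 1.08 |
| 0.75 | 60% | 0.90 |
| 0.5 | 45% | 0.60 |

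**(3) Comparison of arms.** The filter need not reduce power. Assume 60 v 60, an uncorrected chi-square test at two-sided 0.05, and true incidences of 30% v 10%, that is 10% background in both arms plus 20% due to the product. Exact enumeration gives:

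- all events recorded: power 0.802;
- half of all events dropped (15% v 5%): 0.460;
- only half of the background events dropped (5% + 20% = 25% v 5%): 0.898.

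The effect on power has no fixed sign, so no general loss of power is claimed.

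**The case against.** The strongest reply is that the wording is loose rather than restrictive. It does not use the word only, does not say that unrelated events are discarded, and names nobody who screens for cause. Almost any event in a patient taking a study product can be called potentially associated on timing alone, and an open question does not ask about cause. This stands in part: actual loss may be small, and the strict reading is the natural one but not the only one. An open question, however, governs how events are brought out, not which answers are entered. If all events are intended, the text should say so.

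Second, the size depends on assumed pass shares, and 50% fits poorly with a low threshold. That is fair. At 90% the limit moves only from 4.9% to 5.4%, and at 95% only to 0.0487/0.95 = 5.1%. Going from 60 to 50 patients on product (5.8%) matters more than a 90% filter. The figures show how the conclusion depends on an unknown; they do not measure a loss.

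Third, the limits are for one arm and for all-cause incidence, while the argument relies on the placebo comparison, which is weak for rare events. This also stands: at such counts even full recording supports detection of a signal rather than inference. It does not justify a filter, because detecting a signal depends on the event being recorded.

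Last, recording every complaint over 12 weeks of treatment and 24 weeks of follow-up, in patients with many symptoms, adds work at sites whose capacity is limited. That is a real cost, though the question is already to be asked at each visit.

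**Conclusion.** The concern holds. Tolerability is an aim, and the only collection rule makes a possible causal link a condition of entry, so applying the rule as written can remove events that the randomised comparison should be left to interpret.

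The weight is minor to moderate. The primary endpoint is unaffected, no inflation of false positives is claimed, and harms that appear as worse scores are captured anyway. The exposed part is the record of discrete events. If 50% to 90% of them passed the filter, an absence of records among an assumed 60 patients on product would exclude true incidences only above 9.7% to 5.4%, instead of 4.9%. These values rest on the assumed arm size and pass shares. The firm conclusion is that the pass share is unknown under the present wording, so the record cannot be turned into a statement about incidence.

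**What to change.** Replace the sentence on adverse effects in Study development with wording such as: *At every visit an open question will be used to collect all adverse events, whether or not they are thought to be related to treatment; judged relationship will be recorded as a separate field, without knowledge of the assigned arm.* State also that the tolerability comparison by assigned arm is based on all recorded events. A summary of events judged related can be added beside it.

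The cost is this change of wording, somewhat more events to record, one extra field per event, and a relationship judgement made without knowledge of arm. No additional visit or questionnaire is needed.

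### The between-arm comparison names no baseline covariate although the primary-endpoint VAS scores are recorded at treatment start; ANCOVA would usually gain precision at negligible cost

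*Combined protocol and SAP*

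**What the plan says.** All of the analysis text is one sentence under *Calculation of sample size and assessment of results*. It begins "The results obtained will be analyzed by applying the Student t test for independent samples to compare the data between the subjects who" and identifies the two groups as placebo and active recipients. It then adds a second analysis, "with a two-way analysis of variance to compare the data in the subgroups of patients treated with placebo and with VSL#3", without naming the two factors.

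Under *Outcome variables*, "The primary endpoint will be the mean severity of the three main gastrointestinal symptoms reported by patients with fibromyalgia", namely abdominal pain, abdominal bloating and meteorism. No time point is attached, and nothing says whether the quantity analysed is a final score or a change from baseline.

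Under *Study development*, "On the day of initiation of treatment, the following questionnaires will be administered: VAS of abdominal pain, abdominal bloating, meteorism" and the other symptom scales, together with FIQR, ISI, PHQ-9, PGI and SF-36. After that, "VAS of gastrointestinal symptomatology will be filled weekly by the patients during the first 4 weeks of the trial" and every two weeks from week 4 to week 12, with further measurements 4, 12 and 24 weeks after treatment ends.

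On sample size, "the calculation of the sample size is based on the feasibility of recruiting them", and "The recruitment of 120 patients has been estimated as a reasonable attainable goal". No adjusted model appears anywhere in the document.

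**The concern.** A patient's symptom score at treatment start is likely to be among the best predictors of the later score on the same scale. The plan collects it for every component of the primary endpoint and does not say that it will be used.

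What happens to it depends on what is put into the t test. With final scores, the baseline is ignored. With change scores, it is subtracted with a fixed weight of 1, whatever the data say about the slope. ANCOVA estimates that weight.

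None of this biases the randomised comparison. It matters because recruitment limits the trial to about 120 patients, so the analysis is one of the few places left to gain precision. ANCOVA also removes an open choice: with baseline as covariate, the final-score and change-score models give the same treatment difference and the same standard error.

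**Working it through.** There is no power calculation to reproduce, because 120 is a feasibility number. The check compares three analyses under declared assumptions.

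**Inputs**
- From the document: total N = 120; allocation randomised, ratio not stated; baseline VAS available; independent-samples t test.
- Assumed, because the document is silent: 60 analysed per arm (1:1, no dropout), two-sided α = 0.05, true difference 0.5 follow-up SDs, r from 0 to 0.8.

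**Variance factors**, in units of the follow-up variance, with k = SD(follow-up)/SD(baseline):
- t test on final scores: 1
- t test on change scores: 1 + 1/k² − 2r/k, which is 2(1 − r) when k = 1
- ANCOVA: 1 − r²

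At k = 1, ANCOVA's variance relative to the change-score test is (1 − r²)/[2(1 − r)] = (1 + r)/2.

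**Power and precision.** Power comes from the noncentral t with noncentrality 0.5/√(2 × factor/60), on 118 df for the t tests and 117 for ANCOVA. The 95% CI half-width is t(0.975) × √(2 × factor/60). For final scores, power is 77.5% and the half-width 0.362 SD at every r. For k = 1:

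| r | ANCOVA factor | Variance cut vs final | Variance cut vs change | Power, change scores | Power, ANCOVA | ANCOVA half-width (SD) |
|---|---|---|---|---|---|---|
| 0.2 | 0.96 | 4% | 40% | 57% | 79% | 0.354 |
| 0.3 | 0.91 | 9% | 35% | 63% | 81% | 0.345 |
| 0.4 | 0.84 | 16% | 30% | 70% | 84% | 0.331 |
| 0.5 | 0.75 | 25% | 25% | 78% | 88% | 0.313 |
| 0.6 | 0.64 | 36% | 20% | 86% | 92% | 0.289 |
| 0.7 | 0.51 | 49% | 15% | 94% | 97% | 0.258 |

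A simulation of 40,000 trials per value of r agrees: ANCOVA 78.5, 81.0, 83.9, 87.7, 92.3 and 96.8%; change scores 57.2, 62.9, 69.9, 77.4, 85.9 and 93.9%; final scores 77.2 to 78.0%.

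**Equivalent sample size against the final-score test**, 120/(1 − r²): 120/0.91 ≈ 132 at r = 0.3, 120/0.75 = 160 at r = 0.5, 120/0.51 ≈ 235 at r = 0.7.

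**Cost when baseline is uninformative.** Estimating the slope inflates the ANCOVA variance by about 1 + 1/116, or 0.9%, and uses one degree of freedom. At r = 0, power falls from 77.5% to 77.2%. Variance breaks even where (1 − r²)(1 + 1/116) = 1, at r ≈ 0.09. Applying the same inflation across the table lowers ANCOVA power by 0.1 to 0.3 points.

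**Unequal SDs.** The gain over final scores does not depend on k; the gain over change scores does.
- k = 1.25, r = 0.4: 0.84/1.00 = 0.84, a 16% cut.
- k = 1.25, r = 0.7: 0.51/0.52 = 0.98, a 2% cut.
- k = 1.25, r = 0.8: 0.36/0.36 = 1.00, no cut.
- k = 0.8, r = 0.4: 0.84/1.5625 = 0.54, a 46% cut.
- k = 0.8, r = 0.7: 0.51/0.8125 = 0.63, a 37% cut.

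**The case against.** The strongest reply is that nothing here is wrong. The t test is valid, the trial describes itself as a pilot, and no power target is stated that the test could miss. That is right, and it makes this an efficiency point. It does not make the point idle: the plan still names a primary endpoint and a between-arm test, and a pilot also benefits from a tighter effect estimate.

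Second, the size of the benefit is unknown. This stands. At r = 0.2 to 0.3 the gain over final scores is only 2 to 4 power points. At r = 0.7 the gain over change scores is about 3 points, and with unequal SDs it can vanish. The supportable claim is a usual gain at negligible cost.

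Third, the power figures assume no dropout over 12 weeks. With 54 analysed per arm (an illustrative 10% loss), the final-score test has 73.1% and ANCOVA about 75, 77, 80, 84, 90 and 95% for r = 0.2 to 0.7. Absolute power drops; the relative variance gain does not.

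Fourth, the two-way ANOVA might already use baseline. If its factors were arm and time, with time including baseline, the interaction would do so. The text speaks only of subgroups and defines no factors, so this reading cannot be relied on.

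**Conclusion.** The concern holds as an available improvement, not an error. No baseline covariate is named, and the baseline values of all three primary-endpoint components are collected. Against a final-score t test, ANCOVA cuts variance by 4% to 49% for r between 0.2 and 0.7; against a change-score test with equal SDs, by 40% to 15%. The most it loses is under half a power point, at r = 0.

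The omission itself is certain. The size of the gain rests on an r that the documents do not give, and the power figures also rest on 60 analysed per arm, a 0.5 SD difference and two-sided 5% testing. The change is worth making because the potential gain is material at moderate r, the cost is trivial and the sample size is capped.

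**What to change.** Before unblinding, make ANCOVA the primary analysis. Suggested text: *The mean of the abdominal pain, abdominal bloating and meteorism VAS scores at [primary time point] will be compared between arms in a linear model with treatment arm as factor and the mean of the same three scores on the day of treatment initiation as covariate. The adjusted difference will be reported with its 95% confidence interval.*

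The sponsor must fill in the time point, which the plan does not state. Week 12, the end of treatment, is the natural candidate. Use the same form for the individual symptom VAS scores, FIQR, ISI, PHQ-9 and SF-36, each with its own baseline. Keep the t test as a supportive analysis, and say whether it uses final or change scores. Separately, name the two factors of the two-way ANOVA.

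The cost is a few sentences, the decision on the time point, a clarification of the ANOVA and one degree of freedom. No extra patients, visits or measurements are needed.

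### The two-way ANOVA names neither its second factor nor a patient term; run literally as arm by visit on the repeated VAS readings, its arm test would have a false-positive rate far above 5%.

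*Combined protocol and SAP*

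**What the plan says.** The analysis plan is one sentence in the section on sample size and assessment of results. It gives a Student t test for independent samples between the arms, and then continues "with a two-way analysis of variance to compare the data in the subgroups of patients treated with placebo and with VSL#3". It states no second factor, error term, covariance structure, significance level or analysis time point. The primary endpoint under Outcome variables (mean VAS severity of three symptoms) has no time point either.

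The schedule under Study development produces repeated readings from each patient:

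- **VAS.** Taken at the start of treatment ("On the day of initiation of treatment, the following questionnaires will be administered: VAS of abdominal pain, abdominal bloating, meteorism"), then "filled weekly by the patients during the first 4 weeks of the trial and every 2 weeks between weeks 4 and 12".
- **Week 12 scales.** "At week 12, FIQR, ISI, PHQ-9 and quality of life questionnaire will also be completed again".
- **Follow-up.** After treatment ends, "patients will be monitored at 4, 12 and 24 weeks thereafter; these visits will measure VASs of gastrointestinal symptoms, FIQR, PGI and SF-36".

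On size and allocation: "The recruitment of 120 patients has been estimated as a reasonable attainable goal" and "The assignment of the subjects to the group that will receive the active product or the placebo will be randomized". The allocation ratio is not given.

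**The concern.** The t test already compares the arms, so a two-way ANOVA must bring in a second factor. The groups it mentions are the placebo and VSL#3 patients themselves, and no patient-level subgroup variable is defined anywhere. Visit is the factor that the schedule crosses with arm in every patient. The ANOVA is also the only stated method that could take in the whole VAS series, because a t test uses one value per patient.

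If arm by visit is run as a textbook two-way ANOVA, it has a single residual and treats each reading as if it came from a different patient. Between-patient variation then goes to the wrong place. The arm effect is tested against an error that is too small, and the arm-by-visit effect against one that is too large. An ineffective product could look effective through the arm term, and an effect that builds over treatment could be missed through the interaction. The ANOVA could also disagree with the t test, with nothing in the plan to say which to believe.

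**Working it through.** The plan has no figure to reproduce: the sample size rests on feasibility, and no power, effect size or SD is stated. What can be checked is how the ANOVA behaves if it is run literally as arm by visit.

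**Readings per patient (k), from Study development**
- VAS on treatment: weeks 1, 2, 3, 4, 6, 8, 10, 12 = 8. With day 0: 9. With three follow-up visits: 12.
- FIQR and SF-36: day 0, week 12 and three follow-ups = 5 (taking the quality of life questionnaire at week 12 to be the SF-36).
- ISI and PHQ-9: day 0 and week 12 = 2.

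**Assumptions not in the documents**
- 120 patients split 60/60, complete data, equal variances, two-sided 5% level.
- Equal correlation ρ between any two readings of one patient, 0.4-0.7 as the working range and 0.2-0.8 as the wider range.

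**Arm test.** With σ² the variance of a single reading, the pooled residual estimates about σ². Under no treatment effect, the arm mean square has expectation σ²[1 + (k−1)ρ]. The false-positive rate is therefore close to

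2 × {1 − Φ(1.96 / √[1 + (k−1)ρ])}.

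For k = 8 and ρ = 0.4: 1 + 7 × 0.4 = 3.8; √3.8 = 1.949; 1.96/1.949 = 1.005; rate 31.5%. For ρ = 0.7: 1 + 7 × 0.7 = 5.9; √5.9 = 2.429; 1.96/2.429 = 0.807; rate 42.0%.

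| k | ρ = 0.2 | 0.4 | 0.7 | 0.8 |
|---|---|---|---|---|
| 2 | 7.4% | 9.8% | 13.3% | 14.4% |
| 5 | 14.4% | 22.4% | 31.5% | 33.9% |
| 8 | 20.6% | 31.5% | 42.0% | 44.6% |
| 9 | 22.4% | 33.9% | 44.6% | 47.1% |
| 12 | 27.3% | 39.9% | 50.6% | 53.1% |

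Monte Carlo with the F distribution agrees (31.2% and 42.0% for k = 8 at ρ = 0.4 and 0.7). Letting the correlation decay with time, with week-to-week correlation 0.7 to 0.95 and k = 8, gives 25% to 44%.

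**Arm-by-visit test.** Its mean square has null expectation σ²(1−ρ) but is divided by about σ², so the test is conservative. For k = 8, with the effect set so that a correct within-patient analysis has the power shown in the first column, the literal ANOVA has:

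| Correct power | ρ = 0.2 | 0.3 | 0.4 | 0.5 | 0.6 | 0.7 |
|---|---|---|---|---|---|---|
| 80% | 64% | 52% | 37% | 21% | 7% | 1% |
| 90% | 79% | 69% | 54% | 35% | 16% | 3% |

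Its type I error falls from 5% to about 0.17% at ρ = 0.4 and to about zero at 0.7. With two readings and correct power of 80%, about 60%, 51%, 38% and 22% remains at ρ = 0.4, 0.5, 0.6 and 0.7.

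**With a patient term.** Tested against between-patient error, the arm effect has 5% error by construction under these assumptions. The arm-by-visit test returns to 4.9-5.1% in simulation, with its full power.

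**Other readings of the sentence**
- Arm by patient subgroup, one reading per patient: simulated arm false-positive rate 5.0%, so no inflation.
- Separate tests over time within each arm: if a shared placebo response gives each arm probability p of significance, a significant VSL#3 arm beside a non-significant placebo arm arises by chance with probability p(1−p). That is 0.6 × 0.4 = 24% at p = 0.6, near the maximum of 25% at p = 0.5, and 0.9 × 0.1 = 9% at p = 0.9.

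**The case against.** The strongest reply is that the plan never says the ANOVA is an ordinary one or that it lacks a patient term. A reader might infer that the plan has committed to an invalid test with a 31-42% error rate. The documents do not support that, because they leave the factors and the error term open. A repeated-measures two-way ANOVA fits the sentence equally well.

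So does an arm-by-subgroup ANOVA on one value per patient. The introduction distinguishes patients with comorbid irritable bowel syndrome from those with non-specific gastrointestinal symptoms, and the exclusion criteria admit the former, so that status would be a natural factor. Neither alternative has the inflated arm test under the conditions computed. This objection stands, and the figures must be read as conditional.

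A reader might also infer that the interaction test always loses most of its power. That is too strong at correlation 0.2-0.3, at 0.4 when the correct power is 90%, and with two readings at 0.4-0.5.

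Finally, the trial is described as a pilot, the t test is listed first, and nothing makes the ANOVA primary. That lowers the severity. It does not close the gap: no subgroup variable is defined, no repeated-measures structure is stated, and the repeated VAS series is left without a stated valid method.

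**Conclusion.** The concern holds as a conditional one. The second analysis is underspecified in a way that matters. If it is carried out literally as arm by visit on all readings, the arm test's false-positive rate is about 31-42% with 8 readings and correlation 0.4-0.7. It is about 10-13% with two readings, and about 7-53% across 2-12 readings and correlation 0.2-0.8. The arm-by-visit test errs the other way: with 8 readings and a correct power of 80%, about 64% remains at correlation 0.2, 37% at 0.4 and 1% at 0.7.

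Allocation, correlation and significance level are assumptions, but every case of the literal arm-by-visit analysis that was checked puts the arm test above 5%. A t test on one value per patient is not affected. The wording should be corrected before unblinding; the documents do not show that an invalid analysis has been chosen.

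**What to change.** Replace the two-way ANOVA as follows.

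- **VAS, FIQR and SF-36:** a linear mixed model for repeated measures with the baseline value as covariate and arm, visit and arm-by-visit as fixed effects. Use an unstructured within-patient covariance, with a simpler structure stated in advance in case the model does not converge. Read the arm contrast at one pre-named visit, such as week 12.
- **ISI and PHQ-9:** compare the arms at week 12 with one value per patient, adjusted for baseline.
- **Within-arm change:** report descriptively, without p-values.
- **If patient subgroups were meant:** name the baseline variable before unblinding, test the arm-by-subgroup interaction and label it exploratory.

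The cost is about one paragraph of analysis text and slightly more analysis work. The p-values for arm will be less favourable than the literal ANOVA would give. No new data are needed.
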